Evaluation of the effect of anti-inflammatory treatment in patients with depression has not been limited to those with medical illness. As pain and disease effects could be major contributors to depressed mood, some studies have been done to investigate anti-inflammatory efficacy in patients with major depression without major medical comorbidities. In one randomized, double-blind, placebo controlled study celecoxib was given to patients with major depression as an adjunctive treatment to the antidepressant reboxetine (a selective norepinephrine reuptake inhibitor). A much greater improvement in depression symptoms was shown among those receiving celecoxib as the adjunct. In a similar study utilizing celecoxib as an adjunctive agent to antidepressant treatment with fluoxetine, those patients given celecoxib saw significantly greater improvement. In a follow-up study celecoxib used as an adjunctive agent to treatment with sertraline demonstrated both significantly improved depression scores in the celecoxib group and also significantly greater reductions in the inflammatory biomarker IL-6, with significant correlations observed between Hamilton Depression Rating Scale (HAM-D) scores and IL-6 levels. Two meta-analyses of the use of celecoxib as an adjunctive treatment for patients with depression both found in favor of its use. Unfortunately, COX-2 inhibitors such as celecoxib carry an increased risk of ischemic cardiovascular disease, to the extent that related medications rofecoxib and valdecoxib have been withdrawn from most markets. Some analyses support the idea that salicylates and COX-2 inhibitors may separate from other NSAIDs in their relationship to antidepressant response. Given that salicylates like aspirin are ubiquitous, with low cost and a safety profile in long-term use that is well-known, there would be an advantage to the use of salicylates in depression if indeed they prove effective.

There may be other advantages as well: aspirin, unlike the selective agent celecoxib, is technically a ‘nonselective’ inhibitor of cyclooxygenase, although it in fact more potently inhibits COX-1 than COX-2. As there is some evidence that COX-2 has anti-inflammatory and neuroprotective activities in the brain, inhibiting it may not be the optimal target for antidepressant treatments.

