## **III. Subject Selection:**

This study is a randomized, double-blind, placebo-control trial. The trial will enroll 74 adult subjects with treatment-refractory major depressive disorder, 37 per group. Assuming a non-completion rate of approximately 20%, as is customary in clinical trials of antidepressants, we will enroll a total of 74 subjects, anticipating 60 study completers. Subjects will all be recruited through outpatient psychiatric clinics affiliated with Brigham and Women's Hospital, through physician referral, print advertisements, and flyers.

Inclusion criteria:

- Aged 18-55
- Current diagnosis of major depressive disorder
- Hamilton Depression Rating Scale score of  $\geq 21$

- Stable treatment regimen (no medication changes or changes in psychotherapy treatment in past 8 weeks, and no participation in stepped treatments, such as completion of a course of cognitive behavioral therapy, during the trial)
- Failed to remit with up to 2 sequential antidepressant trials, or combination of 1 antidepressant and 1 augmentation agent
- Women of childbearing age must agree to use an approved method of contraception for the duration of the study

Exclusion criteria:

- Active suicidal ideation
- History of manic episodes or psychosis
- Alcohol or substance use disorder within the past 6 months
- Comorbid neurologic condition affecting the central nervous system
- Comorbid autoimmune condition
- History of thyroid disease or a current abnormal TSH
- Active or recent (within the past month) infection (such as otitis, pneumonia, urinary tract infection); temperature  $> 100.3$  or WBC count  $> 11$  K/microL will be considered evidence of active infection even in the absence of other symptoms
- History of GI bleed
- History of stroke
- History of a bleeding disorder
- Platelet count  $< 150,000/\text{mm}^3$  on initial screening
- On a blood-thinning agent or taking NSAIDs daily
- Current use of oral steroids or other immunomodulating medications
- Salicylate sensitivity
- Pregnancy or breastfeeding
- GFR less than  $60 \text{ mL/min}/1.73\text{m}^2$
- Current use of another nephrotoxic medication

The decision not to restrict participation to subjects utilizing a single medication was made to better reflect clinical practice, in which a variety of SSRI (selective serotonin reuptake inhibitors) and SNRI (serotonin-norepinephrine reuptake inhibitors) are used as first-line agents, and in order to enhance the generalizability of study findings.

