### Study Visit 1 (screening and study week 0):

At the first study visit, the principal investigator or co-investigator study physician will obtain informed consent. Details about the study, including objectives, procedures, and potential risks and discomforts will be discussed with the subject by a physician investigator. Subjects will be given the opportunity to ask any questions and will be given ample time to consider whether they wish to participate. They will be informed that refusal to participate will not interfere with their subsequent medical care.

The clinical study staff will then administer the Hamilton Depression Rating Scale (HDRS) and the Mini International Neuropsychiatric Interview (MINI) to confirm the subject has an active diagnosis of major depressive disorder (as defined by DSM V criteria) and rule out diagnoses of exclusion (namely mania, psychosis or hypomania). Subjects with active suicidal ideation, represented by a score of  $>2$  on HDRS item 3, will be ineligible for the study and will be referred for urgent or emergent clinical assessment as indicated in the safety plan. Subjects will complete the Quick Inventory of Depression Symptomatology-Self Report (QIDS-SR), the MGH Antidepressant Treatment Response Questionnaire, the Systematic Assessment for Treatment Emergent Events (SAFTEE), and the Childhood Experience of Care and Abuse Questionnaire (CECA-Q3). The QIDS-SR and SAFTEE are customary for antidepressant medication clinical trials. The CECA documents early life stressors that can both increase risk for depression and impact cytokine levels through the lifespan.

All subjects will have a complete blood count drawn to measure their white blood cell and platelet counts and a thyroid screening hormone test. Subjects will also have labs drawn to measure blood urea nitrogen, creatinine, and electrolytes. Subjects will be asked about co-morbid neurologic, rheumatologic, and bleeding disorders and recent history of infection. Subjects will be asked to report on their use of oral steroid medications, non-steroidal anti-inflammatory drugs (including aspirin, ibuprofen, naproxen, meloxicam, celecoxib, diclofenac, nabumetone, ketoprofen, and indomethacin), warfarin, heparin, and other anticoagulants (including clopidogrel, enoxaparin, rivaroxaban, apixaban, edoxaban, dabigatran, and fondaparinux).

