## **VI. Biostatistical Analyses:**

The baseline data to be collected and analyzed include: subject age at enrollment, gender, age of depression onset, number of previous depressive episodes, HDRS. HDRS will be repeated at the subsequent study visits for analysis. Cytokine levels will also be analyzed at the initial and final visits. The planned study end-point is at eight weeks after initiation, and is not based on any pre-determined treatment response. Exploratory analysis of the immunologic profiling data will be performed as well, with a goal to detect within-subject changes over the course of the study and to discern any differences between non-responders and responders.

Baseline measurements for continuous variables (e.g., age of onset, current age) will be assessed by t-test. Categorical measurements, such as gender, will be compared with Fisher's exact test or chi-square as appropriate. For the primary study outcome, the change in HDRS in the treatment versus control groups will be evaluated with analysis of covariance (ANCOVA), with initial HDRS score as a covariate.

Power calculations were based on a prior open-label trial of salicylic acid as an augmentation agent to fluoxetine, which found an average 15-point drop in HDRS score over a 4-week trial. To be conservative, we are assuming a much smaller effect size, and so this study is powered to detect a 3-point difference in HDRS score, a difference which is deemed to be clinically significant. 29 participants per group are required to detect this clinically significant difference assuming .80 power and a two-sided alpha of 0.05. Assuming a non-completion rate of approximately 20%, customary in clinical trials of antidepressants, we will enroll 74 subjects, anticipating 60 completers.

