Secondary outcomes will include the response of inflammatory biomarkers in treatment responders v. treatment non-responders at 8 weeks and the degree of biomarker association with antidepressant response. For this, the association of IL-6 and TNF- $\alpha$  at V1 with change in HDRS from V1 to V4 in the aspirin treated group versus the placebo treated group will be evaluated with an analysis of covariance (ANCOVA) model. This model will include three variables: treatment condition (aspirin versus placebo), baseline IL-6 or TNF- $\alpha$  level, and an interaction term (baseline cytokine value x treatment). A similar analysis of change in HDRS scores will be performed to assess the interaction of baseline TNF- $\alpha$  to IL-10 and IL-6 to IL-10 ratios by treatment condition. All applicable tests will be two-tailed with an alpha set at 0.05.

For our exploratory analysis of the full panel of 60 cytokines and chemokines, we expect to perform 60 comparisons and plan to use a false discovery rate approach. The interaction of the baseline value of each cytokine or chemokine with treatment condition will be evaluated. The interaction  $p$  values will be converted to FDR *adjusted p* values and ordered from smallest to largest. A cut point of 10% will be used to control the false discovery rate and to identify a subset of values that will be presumed to be biologically relevant. A similar procedure will be carried out for analysis of the 96 immune genes. All analyses were designed in consultation with a biostatistician.

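### The IL-6, TNF-α and ratio moderator models of HDRS change leave out baseline HDRS, which the primary ANCOVA includes; this may give up modest precision in secondary tests that already have low power

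*Combined protocol and SAP*

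**What the plan says.** All the analysis text is in Section VI, Biostatistical Analyses.

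- **Primary outcome.** HDRS change is compared between arms by ANCOVA, "with initial HDRS score as a covariate".
- **Aim 2a.** The outcome is HDRS change from Visit 1 to Visit 4, and the model is fully listed: "This model will include three variables: treatment condition (aspirin versus placebo", followed by baseline IL-6 or TNF-α and the cytokine-by-treatment product. Nothing else enters.
- **Aim 2c.** "A similar analysis of change in HDRS scores will be performed to assess the interaction of baseline" cytokine ratios (TNF-α and IL-6, each to IL-10) by treatment. The terms are not listed again, so the Aim 2a list carries over.
- **Exploratory panels.** For the 60 analytes, "The interaction of the baseline value of each cytokine or chemokine with treatment condition will be evaluated", and the 96 genes are handled similarly. Neither outcome nor covariates are restated.

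Baseline HDRS is available for everyone. Under Study Visit 1, "The clinical study staff will then administer the Hamilton Depression Rating Scale (HDRS", and Section III makes a minimum score of 21 an entry criterion.

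**The concern.** Two models in the same section analyse change in HDRS. One adjusts for the starting score and the other does not, and no reason is given for the difference. The starting score is measured before randomisation and is itself part of the change score, so it will often correlate with change. When it does, leaving it out puts explainable variation into the residual and widens the interval for the cytokine-by-treatment interaction.

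Finding a biomarker that predicts benefit from aspirin is a stated purpose of the trial. The sample size, however, was set for a 3-point main effect, and interaction tests at that size have little power. Precision available from data already in hand is worth taking.

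**Working it through.** **Inputs from Section VI.** 29 per arm (58 in total); two-sided 0.05; Aim 2a terms as listed above. With the intercept, that model has 4 coefficients and 58 − 4 = 54 residual degrees of freedom, or 53 once baseline HDRS is added.

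**Assumed, because the documents do not give them.** The correlation *c* between baseline HDRS and HDRS change; the SDs at baseline and week 8; the size of the interaction.

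**The plan's own figure.** 29/0.80 = 36.25, rounded up to 37 per arm and 74 in total, as stated; 74 × 0.80 = 59.2, close to the plan's 60 completers. No SD is given for the 29, which is consistent with an SD of about 4.0 (a t-test then needs 28.9 per arm). No power or precision figure is given for the moderator models, so there is none to reproduce.

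**Step 1: interval width.** Adding a covariate with correlation *c* multiplies the variance of the interaction estimate by about (1 − c²) × 54/53, and the interval width by the square root of that.

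| Size of c | Variance ratio | Width ratio | Change in width | 58 completers act like |
|---|---|---|---|---|
| 0 | 1.000 × 1.0189 = 1.019 | 1.009 | about +1% | 58/1.019 ≈ 57 |
| 0.20 | 0.960 × 1.0189 = 0.978 | 0.989 | about −1% | 58/0.978 ≈ 59 |
| 0.35 | 0.8775 × 1.0189 = 0.894 | 0.946 | about −5% | 58/0.894 ≈ 65 |
| 0.50 | 0.750 × 1.0189 = 0.764 | 0.874 | about −13% | 58/0.764 ≈ 76 |

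Simulation (20,000 trials per setting, 29 per arm, least-squares interaction test) gave +1.0%, −1.1%, −5.4% and −12.5%.

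**Step 2: validity.** In the same simulations type I error was 4.8–5.2% with or without baseline HDRS, and mean interaction estimates were within 0.01 of the true value in both models.

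**Step 3: power (%), without → with baseline HDRS.** Interactions are in SDs of HDRS change per SD of cytokine. The skewed cytokine is lognormal with log-SD 0.8.

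| Interaction, cytokine | c = 0 | 0.20 | 0.35 | 0.50 |
|---|---|---|---|---|
| 0.3, normal | 19.4 → 19.1 | 19.4 → 19.7 | 19.1 → 20.8 | 19.2 → 23.7 |
| 0.4, normal | 30.0 → 29.6 | 30.2 → 30.7 | 30.9 → 33.9 | 29.9 → 37.5 |
| 0.3, skewed | 16.5 → 16.4 | 16.4 → 16.6 | 15.9 → 17.7 | 16.0 → 19.5 |
| 0.4, skewed | 24.8 → 24.3 | 25.0 → 25.3 | 25.3 → 27.7 | 25.4 → 31.5 |

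**Step 4: which values of c are plausible.** Let k be week-8 SD divided by baseline SD, and r the Visit 1–Visit 4 correlation. Then c = (rk − 1)/√(1 + k² − 2rk).

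| k | r = 0.2 | 0.3 | 0.4 | 0.5 |
|---|---|---|---|---|
| 1.5 | −0.43 | −0.36 | −0.28 | −0.19 |
| 2.0 | −0.29 | −0.21 | −0.11 | 0.00 |

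Over this grid the size of c runs from 0 to 0.43. At 0.43 the width ratio is √(0.815 × 1.0189) = 0.911, so the change runs from about +1% to −9%. A value near 0.5 needs a smaller k: with r = 0.2, c = −0.54 at k = 1.2 and −0.50 at k = 1.3. Equal SDs give −0.63 to −0.50 over r = 0.2 to 0.5.

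The entry floor narrows the baseline spread. Cutting an assumed normal distribution with SD 5 and mean 20, 22 or 24 at 21 leaves an SD of 2.8, 3.2 or 3.6. Week-8 scores face no such floor, which pushes k above 1 and c towards zero.

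**Step 5: cytokine correlated with baseline HDRS.** At an assumed correlation of 0.3, the width changes become +1.0%, −0.9%, −4.9% and −11.6%, with type I error 4.6–5.3%.

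**The case against.** The strongest reply is that nothing here is an error. An unadjusted treatment-by-cytokine test in a randomised trial is valid, the analyses are secondary, the primary analysis is untouched, and the gain may be close to nil. With assumed SDs of 3 and 7 and r of 0.3–0.4, adjustment leaves 98–100% of the variance in place. Even at a correlation of 0.35, power for an interaction of 0.3–0.4 rises by only about 2–3 points, and the tests remain underpowered. All of this stands. It limits the weight of the point but supplies no reason to leave the covariate out.

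A reader might infer more than the documents support:

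- **That the omission biases the moderator test.** The Background reports, from a cited celecoxib–sertraline trial, "with significant correlations observed between Hamilton Depression Rating Scale (HAM-D) scores and IL-6 levels". That concerns another trial and does not show bias here. In Step 5 such a correlation left type I error near 5% and slightly reduced the gain.
- **That the loss is large.** Assuming equal SDs and r = 0.3 gives a variance ratio of 0.65 and an interval about 19% narrower. The documents give no SDs, and the entry floor argues against equality.
- **That Aim 2b is caught by the same fault.** Aims 2a and 2c use continuous HDRS change and need no responder split. Aim 2b, Hypothesis 2b and the reference to 8 weeks in Section VI all point to post-treatment cytokine levels, a different analysis.

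**Conclusion.** The point holds as one of efficiency and consistency, not validity. The omission is explicit for Aim 2a, follows by reference for Aim 2c, and is unexplained. Its effect is conditional: interval width would change by about +1% to −9% over the range of SD ratios and correlations taken as plausible here, reaching −13% only if the baseline–change correlation is near 0.5. That requires a week-8 SD not much above the baseline SD (ratio up to about 1.3, with a low Visit 1–Visit 4 correlation).

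These sizes rest on assumed correlations, SDs and interaction sizes, on 29 completers per arm, and on baseline HDRS acting additively, without itself modifying the treatment effect. No Aim 2a or 2c conclusion is shown to reverse. The change is worth making because it is nearly free and the tests have little power to spare.

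**What to change.** In Section VI, add baseline HDRS as a covariate to the IL-6, TNF-α, TNF-α:IL-10 and IL-6:IL-10 moderator models, as in the primary ANCOVA. State the same covariate for the 60-analyte and 96-gene interaction models wherever HDRS change is the outcome, and settle this before unblinding.

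The cost is a change of wording; no new data are needed. Each model loses one degree of freedom, so if baseline HDRS turns out not to be prognostic, the interval is about 1% wider and power falls by at most about 1 point.

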## **VII. Risks and Discomforts:**

Aspirin is approved for analgesia and its anti-pyretic effect, and is commonly used off-label for a number of other indications including acute coronary syndrome, acute stroke, in coronary disease, and for its anti-inflammatory effect. Unfortunately, accurate estimation of frequencies of adverse effects is deemed not feasible, in part related to some reactions being idiosyncratic. Adverse effects of aspirin are often dose-related. Likely the most important adverse effect associated with aspirin administration is bleeding, which can occur throughout the body; gastrointestinal ulceration occurs in 6 to 31%. Other bleeding-related conditions make up a significant proportion of the remainder of the common adverse effects of aspirin.

There is a possibility that aspirin in combination with antidepressant medications may carry an increased risk of bleeding. For example, epidemiologic studies support an increased risk for upper gastrointestinal (GI) bleeding with selective serotonin reuptake inhibitor (SSRI) use, and this is increased with concurrent use of aspirin. The relative risk of upper GI bleed with an SSRI-aspirin combination in some studies reviewed ranged from 1.9 to 7.2. This is important given the frequency with which SSRI medications are used as first-line agents for depression; it can be expected that many subject participants will be taking a medication in this class or a related class. However, the overall risk remains low: the number needed to harm for a GI bleed with an SSRI-aspirin combination ranged from 81 to 170 patient-years in the studies reviewed. There is also some risk of intracranial hemorrhage. Shin et al examined the 30 day risk of intracranial hemorrhage in Korean patients who took both antidepressants and NSAIDs and found a hazard ratio of 1.6 over use of antidepressants alone. However, as others have pointed out, it is not clear that this risk is related to the combination of the two drugs as there was no control group examined who were not taking an NSAID, suggesting that the effect could be the risk of the NSAID alone rather than a synergistic one. Too, the study was performed with an entirely Korean population, raising the question of generalizability to other populations given ethnic variability in the activity of CYP450 enzymes involved in the metabolism of many antidepressants and non-steroidal. Finally, the increased risk for bleeding was only statistically significant in men. This is relevant to the study population given the preponderance of women affected by depression and the expected higher female to male ratio amongst study participants. How the data above translate into risk for our population is not entirely clear, but one assessment of the number needed to harm if extrapolating from Shin's data found that the combination of antidepressants and NSAIDs gives an additional 4.1 hemorrhages/1000 patient-years, equivalent to one avoidable intracranial hemorrhage in first 30 days per 3000 men starting on the combination. Assuming an equal distribution of men and women, this would mean one avoidable intracranial hemorrhage per 6000 subjects, although as stated above this number is likely to be slightly lower given higher rates of depression in women.

Serotonin-norepinephrine reuptake inhibitors (SNRIs), which are another popular first-line medication for depression, appear to have similar risks for intracranial hemorrhage in depressed patients as compared to SSRIs but do not carry the same risks for gastrointestinal bleeding that SSRIs do. Some studies class all the serotonin blockers together to look at adverse effects and results are inconsistent: for example, in one study of patients taking either SNRIs or SSRIs and warfarin together, the risk of death from intracerebral hemorrhage was higher than with warfarin alone. On the other hand, another study that evaluated patients undergoing coronary artery bypass grafting found no association between taking the combination of either SNRI or SSRI and

anti-platelet treatment (including aspirin) and risk for bleeding. Unfortunately, there are no studies that directly evaluate the effect of aspirin and SNRIs on combined morbidity and mortality risk in a depressed population, so direct extrapolations to our study are challenging.

We were unable to find any studies evaluating the risks associated with bupropion, another commonly used antidepressant and augmenting agent, in combination with aspirin. It is therefore unknown if there is an increased risk of bleeding or other concern in combining bupropion and aspirin. Mirtazapine, often used as a second-line antidepressant and occasionally used as first-line, has been shown to induce platelet antibodies in vitro, but has not been shown to be associated with increased risk for hemorrhage. Whether mirtazapine would be associated with increased risk for bleeding in combination with aspirin is unclear. Overall, there is a lack of published reports on the safety of combining antidepressants other than SSRIs or SNRIs with aspirin. There is no evidence to suggest increased risk of bleeding in combining bupropion or mirtazapine with aspirin.

Of note, and perhaps relevant to all of the above-named antidepressants that are in common use, aspirin is already a commonly given medication for patients with a number of cardiac conditions. Given the prevalence of both cardiovascular disease and depression, it is inevitable that a large number of patients are concurrently being treated with aspirin and a variety of antidepressants. Thus, while the safety of this medication in combination with a range of antidepressants may not have been demonstrated in a clinical trial, there have been ample opportunities for risks associated with these combinations to come to clinical and scientific attention. The lack of publications reporting increased risk is as at least somewhat reassuring as to the relative safety of this combination.

The effect of aspirin on an embryo or fetus can include adverse effects up to and including fetal death. For this reason, women cannot take part in this study if they are pregnant or may become pregnant. While aspirin found in breast milk carries less clear risk, the WHO recommends against long-term therapy; for this reason women cannot take part in this study if they are nursing.

With the blood draws, there are risks of pain and bruising at the phlebotomy site, infection, and lightheadedness.

The assessment of psychiatric history, including depression and substance abuse, can make some people feel uncomfortable as the information is sensitive to some subjects. Some may also be especially concerned about the confidentiality of mental health information. The study staff are trained in mental health assessments, and make every effort to make the subjects comfortable during study visits. All subjects will be assured that their history and responses will be kept confidential within the study, except as required by law, in the case of acute safety concerns, and in any instances as described in the informed consent form.

